8.1.3. Discontinuation of Inadvertently Enrolled Patients

If the Sponsor or investigator identifies a patient who did not meet enrollment criteria and was inadvertently enrolled, then the patient should be discontinued from study treatment, unless there are extenuating circumstances that make it medically necessary for the patient to continue on study treatment. If the investigator and the Sponsor-designated medical monitor agree it is medically appropriate to continue, the investigator must obtain documented approval from the Sponsor medical monitor to allow the inadvertently enrolled patient to continue in the study with or without treatment with the investigational product. Safety follow up is as outlined in Section 2 (Schedule of Activities), Section 9.2 (Adverse Events), and Section 9.4 (Safety) of the protocol.

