8.1. Discontinuation from Study Treatment

8.1.1. *Permanent Discontinuation from Study Treatment*

Patients for whom investigational product should be permanently discontinued, irrespective of the reason, should complete the Post-Treatment Follow-Up and then be permanently discontinued from the study. Section 8.2 provides the list of criteria for permanent discontinuation of patients from study treatment and the study.

Patients discontinuing from the investigational product prematurely for any reason should complete AE and other follow-up procedures per Section 2 (Schedule of Activities), Section 5.1.4 (Post-Treatment Follow-up Period), Section 9.2 (Adverse Events), and Section 9.4 (Safety) of this protocol.

8.1.2. *Temporary Interruption (Withholding) of Study Treatment*

Some possible reasons for temporarily withholding investigational product include, but are not limited to:

- Development of:
 - Serious or opportunistic infections, as described in Section 9.2.3).
 - Hypertension (see Section 9.4.2.1).
 - Latent TB infection (LTBI) (see Section 9.4.5.2).
 - Positive HBV DNA results that are below the level of quantification (see Section 9.4.5.4).
 - Hepatic event or liver test abnormality: Investigational product should be withheld and additional testing performed following consultation with the Lilly-designated medical monitor, if the results of repeat tests following elevated ALT, ALP or total bilirubin level (TBL) include one of the following (Section 9.4.6.1):
 - ALT ≥ 3 x ULN and TBL < 2 x ULN
 - ALP ≥ 2 x ULN and TBL < 2 x ULN
 - TBL ≥ 2 x ULN without increase from baseline in ALT/AST/ALP.
- Surgery: Patients requiring surgery at any time during the study should interrupt administration of the investigational product, beginning 8 weeks before the surgery or as early as possible within 8 weeks of surgery, and resume administration of the investigational product only after complete wound healing.

Cases that may merit temporary withholding of the study treatment should be discussed with the medical monitor. The medical monitor, in consultation with the investigator, will determine when it is appropriate to recommence study treatment.

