9.1. Efficacy Assessments

9.1.1. Primary Efficacy Assessments

The primary efficacy endpoints are the proportion of patients with an sPGA (0,1) with at least a 2-point improvement from baseline at Week 16 and the proportion of patients achieving a $\geq 90\%$ improvement in PASI from baseline (PASI 90) at Week 16.

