6.1. General Considerations

Statistical analysis of this study will be the responsibility of Eli Lilly and Company (hereafter, Lilly) or its designee. The latest version of the Medical Dictionary for Regulatory Activities (MedDRA[®]) will be used.

Analyses and summaries from assessment of endpoints described in the protocol (e.g., described in [Table AMAK.4.1](#) and in Section 4 of AMAK protocol) are planned to be included in the clinical study report (CSR). Analyses and summaries for key safety data are also planned to be included in the CSR. Results from additional efficacy analysis pre-defined below and other safety analyses may also be provided in the CSR, as deemed appropriate. Any analysis or summary not included in the CSR will be available upon request.

Any change to the data analysis methods described in the protocol will require a protocol amendment ONLY if it changes a principal feature of the protocol. Any other change to the data analysis methods described in the protocol and the justification for making the change will be described in the CSR.

Additional exploratory analyses of the data may be conducted, as deemed appropriate. Some of these additional supplementary analyses will be prespecified in a separate supplemental SAP.

Some of the analyses described in this document will be incorporated into interactive display tools instead of or in addition to static displays.

The Schedule of Activities outlined in the protocol specifies the allowable windows for assessments. Assessments performed outside these windows will not be excluded from any analysis.

6.1.1. *Patient Populations for Analysis*

Patient populations are defined in [Table AMAK.6.1](#) along with the analysis they will be used to conduct. Patients will be analyzed according to the treatment to which they were assigned for all populations. [Table AMAK.6.2](#) describes the treatment groups and the comparisons for each study period and the analysis population.

Table AMAK.6.1. Patient Populations for Analysis

Population	Description
All Entered Patients	All patients who signed informed consent.
Induction ITT	All randomized patients, even if the patient does not take the assigned treatment, does not receive the correct treatment, or otherwise does not follow the protocol. Unless otherwise noted, efficacy and health outcomes analyses for the induction period will be conducted on this population.

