6.3. Handling of Dropouts or Missing Data

Intercurrent events (ICH E9R1) are events which occur after the treatment initiation and make it impossible to measure a variable or influence how it should be interpreted. Examples of such events include treatment discontinuation due to death or adverse events (AEs), rescue treatment, and loss to follow-up. The missing data methods described below handle intercurrent events in different ways.

6.3.1. *Non-Responder Imputation (NRI)*

The NRI method can be justified based on the composite strategy (ICH E9R1) for handling intercurrent events. In this strategy patients are defined as responders only if they meet the clinical requirements for response at the predefined time AND they remain on the assigned study treatment. Failing either criteria by definition makes them non-responders.

Analysis of binary efficacy and health outcome variables will be assessed using an NRI method. Patients will be considered as non-responder for the NRI analysis if they do not meet the clinical response criteria or have missing clinical response data at the analysis time point. Randomized patients with no postbaseline observations will also be defined as non-responders for the NRI analysis.

For the Maintenance Period, patient who relapse (see definition in [Table AMAK.6.5](#)) after re-randomization during the maintenance period will be considered to have entered the relapse period and will be non-responders for all subsequent visits of maintenance efficacy analysis.

For the Relapse Period, the response rates will be summarized by the weeks after relapse based on the number of patients with planned scheduled visit during the Relapse Period. Patients who complete the Week 52 treatment visit will, thereafter, not be counted in the numerator when calculating the response rate.

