		Time to first regaining PASI 90 or PASI 100 (i.e., 2 different analyses) after relapse	For patients who are observed to regain response during the Relapse Period, time will be from the start of the Relapse Period to the first measurement date where response was achieved.	Patients who are not observed to regain response will be censored after the date of their last visit during the Maintenance Period.
		Cumulative time with PASI 90 response after re-randomization through Week 52	Area under the curve (AUC) of PASI 90 response over time using trapezoidal rule (i.e. 100% when patients are PASI 90 responders at the visit and 0% when patients are non PASI 90 responders at the visit.) percentages of scheduled visits with PASI 90 response among all scheduled visits percentages of weeks with PASI 90 response	NRI if the observed value is missing.
		Relapse	The loss, at any visit, of $\geq 50\%$ of the Week 16 PASI improvement from baseline. That is, a patient will have relapsed during the Maintenance Period if their PASI score increases to greater than or equal to the midpoint between their baseline and Week 16 PASI score.	Missing if baseline, Week 16 or observed value is missing.
sPGA	Static Physician Global Assessment (sPGA): the physician's global assessment of the patient's psoriasis lesions at a given time point. Plaques are assessed for induration, erythema, and scaling, and an overall rating of psoriasis severity is given using the anchors of: clear (0), minimal (1), mild (2), moderate (3), severe (4), or very severe (5).	sPGA score	Range from 0 to 5: clear (0), minimal (1), mild (2), moderate (3), severe (4), or very severe (5).	Single item, missing if missing.
		sPGA (0,1) (Primary)	An sPGA assessed as either 0 or 1, which represents a clinically meaningful response of minimal plaque severity or complete resolution of plaque psoriasis.	Missing if sPGA is missing.
		sPGA (0)	An sPGA assessed as 0, which represents a clinically important endpoint indicating complete resolution of plaque psoriasis.	Missing if sPGA is missing.

Measure	Description	Variable	Derivation/Comment	Definition of Missing Components

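### The SAP's working rules drop two conditions that its own response definitions require: the 2-point sPGA improvement and being on assigned treatment. Few patients can be affected.

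*Protocol*

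**What the plan says.** **sPGA endpoint.** Protocol 9.1.1 names as a primary endpoint the "proportion of patients with an sPGA (0,1) with at least a 2-point improvement from baseline at Week 16". Protocol 10.3.3.1 and SAP Table AMAK.4.1 carry the same 2-point requirement. The row of SAP Table AMAK.6.5 marked as the primary sPGA variable reads "An sPGA assessed as either 0 or 1, which represents a clinically meaningful response of minimal plaque severity" or complete resolution. It does not refer to baseline, and the variable is missing only when the visit's sPGA is missing. SAP 6.5 gives this endpoint all of the initial alpha.

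**Non-responder imputation.** The strategy paragraph of SAP 6.3.1 says that responders must meet the clinical requirements "AND they remain on the assigned study treatment. Failing either criteria by definition makes them non-responders". The paragraph after it gives the working rule: patients are non-responders "if they do not meet the clinical response criteria or have missing clinical response data at the analysis time point", as are randomized patients with no postbaseline observation. Protocol 10.3.1.1 states the same short rule.

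**Who is analysed.** The Induction ITT population (SAP Table AMAK.6.1) is every randomized patient, "even if the patient does not take the assigned treatment, does not receive the correct treatment, or otherwise does not follow the protocol".

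**Patients enrolled in error.** Under protocol 8.1.3 the default is that, once the error is found, "then the patient should be discontinued from study treatment, unless there are extenuating circumstances that make it medically necessary" to go on. By exception, documented approval may be given "to allow the inadvertently enrolled patient to continue in the study with or without treatment with the investigational product". Under 8.1.1, patients whose drug is permanently stopped, "irrespective of the reason, should complete the Post-Treatment Follow-Up and then be permanently discontinued from the study".

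**The concern.** A programmer builds the analysis variables from Table AMAK.6.5 and the working imputation rule, not from the objectives table or a paragraph on estimand strategy. In both places the operational text is looser than the definition it should implement, so the same data allow two values of a primary response rate.

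The SAP writes such conditions out elsewhere. Its combined DLQI and PatGA response variables include the required improvement. Its PASI stability variable treats a patient as missing after study treatment stops. SAP 6.3.1 itself spells out that relapse in the Maintenance Period means non-response. The primary sPGA row has no improvement clause, and the working rule has no clause for stopping treatment.

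Two safeguards normally hide the gaps. Eligibility requires sPGA of 3 or more, which makes the 2-point condition automatic. Leaving the study after stopping drug (8.1.1) makes later data missing, which already means non-response. A patient enrolled in error can fall outside the first safeguard, and the exception in 8.1.3 may take a patient outside the second.

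The sensitivity analyses do not settle the scoring. The tipping-point analysis varies only missing responses, and these would be observed. The per-protocol set may drop some of these patients, but it leaves the ITT result ambiguous, and its exclusion list is in a separate document.

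**Working it through.** **1. The plan's own figure.** Inputs from protocol 10.1: 400 and 100 patients; sPGA 70% v 5%; PASI 90 70% v 3%; two-sided chi-square at 5%; stated power above 95%. Power is Φ[(Δ − 1.96·SE0)/SE1], with SE0 pooled and SE1 unpooled.

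- sPGA: pooled rate (280 + 5)/500 = 0.57. SE0 = √(0.57 × 0.43 × 0.0125) = 0.0554. SE1 = √(0.70 × 0.30/400 + 0.05 × 0.95/100) = 0.0316. (0.65 − 0.1085)/0.0316 = 17.1.
- PASI 90: pooled rate 283/500 = 0.566. SE0 = 0.0554, SE1 = 0.0286. (0.67 − 0.1086)/0.0286 = 19.6.

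Both give power above 99.9%, so the stated figure reproduces.

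**2. When the 2-point condition changes a score.**

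| Baseline sPGA | Week 16 sPGA 0 | Week 16 sPGA 1 |
|---|---|---|
| 3, 4 or 5 | responder under both | responder under both |
| 2 | responder under both (falls by 2) | SAP derivation: responder; protocol: non-responder |
| 0 or 1 | SAP derivation: responder; protocol: non-responder | SAP derivation: responder; protocol: non-responder |

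Inclusion criterion [1]B requires sPGA of 3 or more at screening and baseline, so only patients enrolled in error can differ. PASI 90 is not involved.

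**3. When the treatment condition changes a score.**

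| Patient at the analysis visit | SAP 6.3.1 definition | Working rule |
|---|---|---|
| On drug, criterion met | responder | responder |
| Criterion not met, on or off drug | non-responder | non-responder |
| Permanently off drug, no data | non-responder | non-responder |
| Permanently off drug, criterion met | non-responder | responder |
| Drug temporarily withheld (8.1.2), criterion met | not settled | responder |

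Only the fourth row is a direct conflict. It can affect either primary endpoint.

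**4. Effect per patient at Week 16.** Placebo: 1/100 = 1.0 point. Mirikizumab: 1/400 = 0.25 point. One placebo patient scored either way is the difference between 3% and 4% for PASI 90, or 5% and 6% for sPGA. The stricter wording can only lower a rate.

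**5. Effect on the comparison.** The documents do not give the number affected, so the counts below are assumptions. Each count is mirikizumab patients changed from responder to non-responder, with placebo unchanged.

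| Changed | Mirikizumab rate | sPGA difference | PASI 90 difference (treatment condition only) |
|---|---|---|---|
| 2 (0.5%) | 69.5% | 64.5 | 66.5 |
| 4 (1%) | 69% | 64 | 66 |
| 8 (2%) | 68% | 63 | 65 |
| 20 (5%) | 65% | 60 | 62 |
| 40 (10%) | 60% | 55 | 57 |

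Power stays above 99.9% in every row. At the planned rates, with an uncorrected chi-square, 234 (sPGA) or 245 (PASI 90) of the 280 expected mirikizumab responders would have to change before p reached 0.05. That leaves 46/400 v 5/100 (p = 0.055) or 35/400 v 3/100 (p = 0.052).

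**The case against.** The strongest reply is that both conditions are already in the SAP. The treatment condition stands in 6.3.1 itself as an explicit definition. The 2-point condition is in Table AMAK.4.1, and SAP Section 4 says endpoints are listed in Tables AMAK.4.1, 6.5 and 6.6 together. This stands to the extent that neither condition is absent. What remains is a conflict between definition and working text. It still needs repair, because the working text is complete enough to be programmed as it stands.

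The second reply is that an off-drug patient would have no Week 16 value. Note s to the protocol's Schedule of Activities and Section 5.1.4 send a patient who stops drug early to the early termination visit and then post-treatment follow-up. Section 8.1.3 itself points only to safety follow-up. SAP Table AMAK.6.3 ends the Induction Period at treatment discontinuation or the last treatment visit. This largely stands: no text schedules a Week 16 or Week 52 efficacy visit for a patient permanently off drug. But 8.1.3 does let a patient continue in the study without drug, and no text says that such a patient is not assessed. The conflict is therefore conditional on that assessment taking place.

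A reader might infer more than the documents support:

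- *That 8.1.3 generally keeps ineligible patients in the study.* Its default is to stop drug, and continuation needs agreement and documented approval. Protocol Section 6 also bars prospective waivers. ITT membership comes from the population definition, not from 8.1.3.
- *That both gaps concern the same patients.* One concerns low baseline sPGA, on or off drug. The other concerns patients off drug at any baseline. A patient ineligible for another reason who stays on drug is scored correctly now.
- *That response rates would shift by 1 to 2 points per arm.* This takes 1–2% of 500 patients (5–10, split 4:1 into 4–8 and 1–2) as retained, and has every one of them in an affected subset, assessed and responding. No document gives that frequency. At a 3% placebo PASI 90 rate, 1–2 placebo patients would yield 0.03–0.06 expected responders.

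**Conclusion.** The point holds as an inconsistency in primary-endpoint scoring with a small effect. The primary sPGA derivation in SAP Table AMAK.6.5 does not match the protocol's endpoint, and the working imputation rule does not implement the composite definition that SAP 6.3.1 states. The first matters only for ITT patients enrolled in error with baseline sPGA of 2 or lower. The second matters only for patients permanently off drug with an observed response at the analysis visit; retention without drug under 8.1.3 is an example, if the patient is assessed then.

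The number of such patients is unknown. The reported rates and risk difference could depend on which wording is programmed, but power and the superiority conclusion do not change at the planned rates. Separately, 8.1.1 and the off-drug branch of 8.1.3 contradict each other.

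**What to change.** 1. **SAP Table AMAK.6.5, primary sPGA row:** add that response also needs an improvement from baseline of 2 points or more, and that the variable is missing if either the baseline or the visit sPGA is missing.
2. **SAP 6.3.1, working rule:** add as non-responders those who have permanently discontinued the assigned study treatment before the analysis time point. This follows the SAP's own definition. The word permanently also makes clear that temporary withholding alone is not failure. Align protocol 10.3.1.1.
3. **Protocol 8.1.1 and 8.1.3:** reconcile the two, and state whether a patient retained without drug has efficacy visits. Which rule should govern is for the sponsor to decide.

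The cost is two SAP clauses, one matching protocol edit and one clarification. No new data are needed. Response rates can only stay the same or fall slightly. The changes should be in place before Week 16 efficacy data are unblinded.

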8.2. Discontinuation from the Study

Patients should permanently discontinue the investigational product, complete the Post-Treatment Follow-up, and then permanently discontinue from the study for any of the following reasons:

- **Subject Decision**
 - The patient requests to be either discontinued from the investigational product or withdrawn from the study.
- **Discontinuation due to a hepatic event or liver test abnormality.** Patients who are discontinued from investigational product due to a hepatic event or liver test abnormality should have additional hepatic safety data collected via eCRF.

Discontinuation of the investigational product for abnormal liver tests should be considered by the investigator when a patient meets one of the following conditions after consultation with the Lilly-designated medical monitor:

- ALT or AST >8x ULN
- ALT or AST >5x ULN for more than 2 weeks
- ALT or AST >3x ULN and TBL >2x ULN or international normalized ratio (INR) >1.5
- ALT or AST >3x ULN, with the appearance of fatigue, nausea, vomiting, right upper-quadrant pain or tenderness, fever, rash, and/or eosinophilia (>5%)
- ALP >3x ULN
- ALP >2.5x ULN and TBL >2x ULN

- ALP >2.5x ULN, with the appearance of fatigue, nausea, vomiting, right quadrant pain or tenderness, fever, rash, and/or eosinophilia (>5%)
- In addition, patients who meet any one of the following criteria should be discontinued from the investigational product, enter the Post-Treatment Follow-Up Period, and discontinue from the study:
 - Total white blood cell (WBC) count <2000 cells/ μ L (<2.00 x 10³/ μ L or <2.00 GI/L).
 - Lymphocyte count <500 cells/ μ L (<0.50 x 10³/ μ L or <0.50 GI/L).
 - Platelet count <50,000 cells/ μ L (<50 x 10³/ μ L or <50 GI/L).
 - Changes in blood pressure (BP) (systolic BP at \geq 160 mm Hg plus \geq 20 mm Hg increase from baseline [Week 0; Visit 2]; and/or diastolic BP at \geq 100 mm Hg plus \geq 10 mm Hg increase from baseline) that do not respond following maximal allowed intervention (further explanation in Section 9.4.2.1).
 - The patient experiences a severe AE, an SAE, or a clinically significant change in a laboratory value that, in the opinion of the investigator, merits the discontinuation of the investigational product.
 - Clinically significant systemic hypersensitivity event following administration of investigational product.
 - The patient becomes pregnant.
 - The patient develops a malignancy (Note: patients may be allowed to continue if they develop no more than 2 non-melanoma skin cancers during the study).
 - Any patient who has a change in disease phenotype at any time (for example, a change to pustular psoriasis).
 - If the patient remains at or above their baseline sPGA score at Week 16 (Visit 7) and Week 24 (Visit 9), or remains at or above their baseline PASI score at Week 16 (Visit 7) and Week 24 (Visit 9).
 - It is recommended that the patient be assessed by an appropriately trained professional to assist in deciding whether the patient is to be discontinued from study treatment and the study if:
 - i. The patient, at any time during the study, scores a 3 for Item 12 (Thoughts of Death or Suicide) on the 16-item Quick Inventory of Depressive Symptomatology (QIDS-SR16);

OR

- ii. Develops active suicidal ideation with some intent to act with or without a specific plan (“yes” to question 4 or 5 on the “Suicidal Ideation” portion of the C-SSRS);
OR
- iii. Develops suicide-related behaviors as recorded on the C-SSRS.
 - The patient develops active TB or HIV/AIDS during the study.
 - The patient becomes HBV DNA or HCV RNA positive. The patient should be referred to a specialist physician (see Sections 8.1.2 and 9.4.5.4 for HBV, and Section 9.4.5.5 for HCV).
- Patients will also be permanently discontinued from study drug, complete Post-Treatment Follow-up, and then permanently discontinued from the study in the following circumstances:
 - Enrollment in any other clinical study involving an investigational product or enrollment in any other type of medical research judged not to be scientifically or medically compatible with this study
 - Participation in the study needs to be stopped for medical, safety, regulatory, or other reasons consistent with applicable laws, regulations, and GCP
 - Investigator decision
 - The investigator decides that the patient should be discontinued from the study
 - If the patient, for any reason, requires treatment with another therapeutic agent that has been demonstrated to be effective for treatment of the study indication, discontinuation from the study occurs prior to introduction of the new agent

Patients permanently discontinuing from investigational product, completing the Post-Treatment Follow-Up, and permanently discontinuing from the study prematurely for any reason should complete AE and other safety follow-up per Section 2 (Schedule of Activities), Section 5.1.4 (Post-Treatment Follow-up Period), Section 9.2 (Adverse Events), and Section 9.4 (Safety) of this protocol.

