9.4.6.1. Hepatic Safety Monitoring

If a study patient experiences elevated ALT ≥ 3 x ULN, ALP ≥ 2 x ULN, or elevated TBL ≥ 2 x ULN, liver testing (Appendix 6) should be repeated within 3 to 5 days including ALT, AST, ALP, TBL, direct bilirubin, gamma-glutamyl transferase, and creatine kinase to confirm the abnormality and to determine if it is increasing or decreasing. If the abnormality persists or worsens, clinical and laboratory monitoring should be initiated by the investigator and in consultation with the study medical monitor. Monitoring of ALT, AST, TBL, and ALP should continue until levels normalize or return to approximate baseline levels.

Hepatic Safety Data Collection

Additional safety data should be collected via the eCRF if 1 or more of the following conditions occur:

- Elevation of serum ALT to ≥ 5 x ULN on 2 or more consecutive blood tests
- Elevated serum TBL to ≥ 2 x ULN (except for cases of known Gilbert's syndrome)
- Elevation of serum ALP to ≥ 2 x ULN on 2 or more consecutive blood tests
- Patient discontinued from treatment due to a hepatic event or abnormality of liver tests
- Hepatic event considered to be a SAE

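### AST counts towards discontinuation in Section 8.2 but does not trigger the Section 9.4.6.1 retest, so an isolated AST rise can go 56 days without a protocol-specified recheck

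*Protocol*

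**What the plan says.** Protocol Section 8.2 sets out liver-test conditions for stopping study drug. They are conditions for judgement: "Discontinuation of the investigational product for abnormal liver tests should be considered by the investigator", after consulting the medical monitor. Four of them name AST together with ALT:

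- above 8x ULN;
- "ALT or AST >5x ULN for more than 2 weeks";
- above 3x ULN with TBL above 2x ULN or INR above 1.5;
- above 3x ULN with listed symptoms or eosinophilia.

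Section 9.4.6.1 governs rechecking. Its trigger sentence opens "If a study patient experiences elevated ALT" (3x ULN or more) and continues with ALP ≥2x and TBL ≥2x ULN. Once triggered, "liver testing (Appendix 6) should be repeated within 3 to 5 days". The repeat panel includes AST and creatine kinase, but AST is not among the values that start it. If the abnormality persists or worsens, monitoring begins, and "Monitoring of ALT, AST, TBL, and ALP should continue until levels normalize or return to approximate baseline levels". No interval is given.

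Section 8.1.2 (temporary withholding) refers to the same repeat tests and names ALT, ALP and TBL as the starting values.

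The chemistry row of Table AMAK.1 has on-treatment draws at Weeks 2, 4, 8, 16, 24, 32, 40, 48 and 52. There are none at Weeks 12, 20, 28, 36 or 44. Footnote l allows unscheduled panels at the investigator's discretion.

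**The concern.** A criterion based on duration needs a second measurement. For ALT, the first high value starts a retest within days and then open-ended monitoring. For AST alone, neither follows. The protocol therefore asks whether AST has stayed above 5x ULN for more than 2 weeks, but in one pattern it specifies no sample from which to answer until the next scheduled chemistry visit.

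The pattern is an isolated, asymptomatic AST rise with ALT <3x, ALP <2x and TBL <2x ULN. What is at stake is timely follow-up of a possible liver signal, and whether such follow-up is uniform across sites. After a Week 8 rise, patients on mirikizumab are due an active Week 12 dose before the next scheduled chemistry. In maintenance, active Q8W doses fall at the chemistry visits and most of the injections between them are placebo, so the added exposure there is smaller.

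**Working it through.** **Step 1: where AST stands in each rule**

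| Rule | Is AST a starting value? |
|---|---|
| Section 8.2, four discontinuation conditions | Yes, with ALT |
| Section 9.4.6.1, 3-to-5-day retest | No (ALT, ALP, TBL) |
| Section 8.1.2, withholding after repeat tests | No (ALT, ALP, TBL) |
| Section 9.4.6.1, extra hepatic eCRF data | No; the transaminase item opens "Elevation of serum ALT to" and does not mention AST |
| Section 9.4.5.4, HBV DNA test in HBcAb+ patients | Yes, with ALT, above 3x ULN |
| Section 9.4.5.5, HCV RNA test | No (ALT) |
| SAP Section 6.13.8.1, tabulated elevations | Yes, with ALT |

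The documents are not uniform on AST.

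**Step 2: which Section 8.2 condition depends on a timed second sample**

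AST above 8x ULN meets a condition on one sample. AST above 3x ULN with symptoms or eosinophilia does so at presentation. If TBL is above 2x ULN, TBL itself starts the retest. The persistence condition is the one that turns on time, and for an isolated, asymptomatic rise it matters for AST above 5x and up to 8x ULN.

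**Step 3: days to the next scheduled chemistry**

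Inputs are the visit days and tolerances in Table AMAK.1. The printed days are reproduced by 7 × week + 1 (Week 8: 7 × 8 + 1 = 57; Week 16: 113). The tolerance is ±3 days at Weeks 2 and 4, and ±5 days from Week 8.

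Nominal gap = later day − earlier day. Shortest gap = (later day − tolerance) − (earlier day + tolerance). Longest gap = (later day + tolerance) − (earlier day − tolerance).

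| Interval | Nominal | Shortest | Longest |
|---|---|---|---|
| Week 2 to 4 | 29 − 15 = 14 | 26 − 18 = 8 | 32 − 12 = 20 |
| Week 4 to 8 | 57 − 29 = 28 | 52 − 32 = 20 | 62 − 26 = 36 |
| Week 8 to 16 | 113 − 57 = 56 | 108 − 62 = 46 | 118 − 52 = 66 |
| Weeks 16 to 24, 24 to 32, 32 to 40, 40 to 48 | 56 each | 46 | 66 |
| Week 48 to 52 | 365 − 337 = 28 | 360 − 342 = 18 | 370 − 332 = 38 |

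Five of the nine post-baseline on-treatment draws are followed by a 56-day gap. Measured from the 2-week mark, the next scheduled test comes 46 − 14 = 32 to 66 − 14 = 52 days late.

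**Step 4: effect of adding AST to the trigger**

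The recheck would be due in 3 to 5 days instead of 46 to 66, which is 46 − 5 = 41 to 66 − 3 = 63 days sooner. A 3-to-5-day retest cannot by itself show more than 14 days of persistence. That still depends on the later monitoring, which has no stated interval for either enzyme.

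**The case against.** The strongest reply is that this is a considered choice covered by clinical judgement. The operational rules (retest, withholding, eCRF data, HCV RNA) leave AST out as a starting value. Yet the retest panel measures AST and creatine kinase, and the bilirubin limb of Section 8.1.2 mentions AST. The authors plainly had AST in view. Section 8.2 is a list for consideration, so it need not carry a test clock for every entry.

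Several routes also allow earlier action:

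- Section 9.2 requires documented review of every laboratory report.
- Table AMAK.1 footnote l permits unscheduled chemistry.
- Appendix 6 tests may be obtained for a treatment-emergent hepatic abnormality.
- Section 8.1.2 says "Cases that may merit temporary withholding of the study treatment should be discussed with the medical monitor".
- Section 8.2 allows stopping for "a clinically significant change in a laboratory value that, in the opinion of the investigator, merits the discontinuation of the investigational product".

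Much of this stands. The omission may be deliberate, although no reason is given. The listed routes make an early recheck possible and, for a marked rise, quite likely. But none of them requires a repeat liver test at a set time. The HBV DNA rule covers only HBcAb+ patients, and the test it requires is HBV DNA, not a repeat enzyme measurement.

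It also stands that the missing timed 2-week sample is not peculiar to AST. An ALT above 5x ULN gets the early retest, but no sample fixed just after day 14 either. A reader might infer that the persistence condition works fully for ALT and fails only for AST. The documents do not support that: what AST lacks, and ALT has, is the early retest and the monitoring that follows it.

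**Conclusion.** The mismatch is real and narrow. Section 8.2 uses AST in four conditions. Section 9.4.6.1 does not let AST start a retest, so an isolated, asymptomatic AST rise found at Week 8, 16, 24, 32 or 40 has no required liver recheck for 56 days (46 to 66 with windows). This rests on the chemistry row and visit windows of Table AMAK.1, on the patient staying on schedule without an early termination visit, and on no one using the discretionary routes.

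Three stronger readings are not supported:

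- **That such patients would go unmonitored for 8 weeks.** Earlier testing is open to the investigator; it is simply not required.
- **That 400 of 500 patients are affected.** That is the planned number due an active Week 12 dose between the Week 8 and Week 16 tests. The documents give no frequency for this AST pattern, and none is assumed here.
- **That reported results are compromised.** SAP Section 6.13.8.1 tabulates AST at 3x, 5x and 10x ULN whether or not the rise persists. No efficacy conclusion is affected.

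This is a cheap safety improvement that the sponsor should make; it is not a fault that undermines the trial.

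**What to change.** 1. In Section 9.4.6.1, change the retest trigger to: ALT or AST ≥3x ULN, ALP ≥2x ULN or TBL ≥2x ULN.
2. In Section 8.1.2, align the cross-reference to: repeat tests following elevated ALT, AST, ALP or TBL. Do not add an AST-only withholding limb. Without this step the two sections would disagree on what starts the repeat tests.
3. Optional: in Section 9.4.6.1, state that if ALT or AST remains above 5x ULN at the retest, one monitoring sample is taken just after day 14. The existing 2-week condition can then be judged for either enzyme.

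Section 8.2 needs no change.

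The cost is wording in two sections and one extra panel per isolated AST rise, which may need an unscheduled visit. If the rise persists, the monitoring already prescribed in Section 9.4.6.1 follows until levels return to normal or near baseline, so the number of draws has no fixed cap. The optional sample would also apply to ALT. Some of the added testing will be for AST rises of non-hepatic origin; creatine kinase, already in the retest panel, helps to identify them.
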